In the retrospective chart review, we will collect resource utilization and health care outcome data from 300 infants born 12-18 months prior to the start of the study who had a genetic evaluation, but did not receive NewbornDx and rWGS. We chose infants born in this timeframe to minimize differences between contemporary clinical practice and clinical practice received by our retrospective cohort, hence maximizing the generalizability of our retrospective data to contemporary settings.

Simulation: Extending outcome estimates to a lifetime time horizon

Following data collection, we will use simulation modeling to estimate outcomes (cost, and health outcomes) for all strategies: NewbornDx, rWGS and standard of care diagnostic testing over a 1-year and lifetime horizon. For each strategy, the simulation model will project disorder progression based on estimated health state transition probabilities. By associating each health condition (or “health state”) with a “utility weight” (QALYs gained per year in that state) and annual cost, the simulation will track hypothetical infants and sum QALY gains and incurred costs. Repeating this process with a large number of simulated infants will yield estimated population health and cost outcomes. Costs and utility weights will be estimated from trial data, and previously published estimates, making the assumption that these values depend only on the infant’s health state and not on the diagnostic testing technology. Thus, we assume that the costs and utility weight estimates apply to infants undergoing any of the three diagnostic testing approaches.

Since NewbornDx and rWGS will identify a large number of disorders, disorders will be grouped based on estimated life expectancy and long-term severity. We will identify “disorder groups” by reviewing available data and literature on the expected outcomes of each identifiable disorder in conjunction with expert clinical judgment. We will also identify health states that appropriately represent the possible outcomes for each “disorder group” following review and synthesis of available evidence with input from our Steering Committee and DSMB.

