Our lifetime simulation model will require: 1) classification of health states that describe health outcomes associated with each study strategy (e.g. disorder, disability, death); 2) health state transition probabilities, which represent the likelihood that simulated patients will develop specific disorder and disability outcomes, conditional on their assigned strategy; 3) health state costs, which include both health care associated with a specific health state and other societal costs; and 4) health state utilities, which represent health state preferences for avoiding adverse health outcomes. For the time period extending beyond the 1-year CGA trial duration, we will identify model transition probabilities, health state costs, and health utilities from existing primary datasets and the literature. For many genetic disorders, the literature reports limited long-term follow up data that appropriately account for expected differences in health outcomes due to differences in time to diagnosis. Available data will guide short-term extrapolation beyond our trial timeframe. For long-term time periods for which there are no informative data, we will draw on expert opinion, and conduct appropriate sensitivity analyses to characterize the impact of the attendant uncertainty. Health state costs will include the health care and societal costs (e.g. family costs, special education). We will estimate health care utilization, family time and other resources use for each health state from available data sources and then multiply these utilization estimates by national unit prices. We will also estimate child health state utilities using available data and will include utility values for parental quality of life when possible.

Cost-effectiveness analysis: With simulation findings corresponding to the 1-year CGA trial follow-up period and for extrapolation to a lifetime horizon, we will: 1) calculate

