aggregate population costs and health outcomes (QALYs) for each trial strategy; 2) rank the strategies from least to greatest aggregate population health (total QALYs); and 3) calculate incremental QALYs and costs for the second strategy (compared to the first) and for the third strategy (compared to the second). Incremental QALYs are, by our sequencing of these comparisons, non-negative. If corresponding incremental costs are likewise non-negative, an incremental cost-effectiveness ratio (ICER) (incremental costs divided by incremental QALYs) will be calculated in a similar fashion. If incremental costs are negative in either case – that is, if either strategy reduces costs while improving health relative to its comparator – we refer to this strategy as “cost-saving”.

Secondary Endpoint	Definition	Scale	Populations for which the analysis will be conducted
Satisfaction of the web-based clinical reference database	Usefulness of information Ease of use of the clinical reference database	Categorical	Medical providers who use the clinical reference database after it is built

In order to qualitatively assess the impact of the intervention, we will collect surveys from medical providers across all sites. This survey will be submitted to the IRB prior to implementation.

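### The cost-saving label in section 9.4.3 rests on the sign of point estimates, and no uncertainty is planned for incremental costs, QALYs or ICERs

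*Combined protocol and SAP*

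**What the plan says.** Section 9.4.3 of the combined protocol and SAP sets out three steps, applied to simulation results for the 1-year period and for a lifetime: total costs and QALYs per strategy, a ranking by total QALYs from lowest to highest, and increments of the second strategy over the first and the third over the second. It states the consequence of the ranking openly: "Incremental QALYs are, by our sequencing of these comparisons, non-negative". An ICER is calculated when the incremental cost is also non-negative. The cost-saving label follows "If incremental costs are negative in either case", and is explained as the situation "if either strategy reduces costs while improving health relative to its comparator".

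On uncertainty, the section says of the model: "Repeating this process with a large number of simulated infants will yield estimated population health and cost outcomes". Its one further commitment is: "For long-term time periods for which there are no informative data, we will draw on expert opinion, and conduct appropriate sensitivity analyses". No method is named for those sensitivity analyses.

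The objectives table in section 3 and the endpoint list in 9.4.3 define both economic endpoints as NewbornDx and rWGS compared with SOC testing.

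**The concern.** The label makes a claim about two quantities, lower cost and better health, and neither carries a measure of error. The health half is met by construction, because the strategies are sorted on the estimated QALYs before they are differenced. The cost half is met by any estimate below zero, however small.

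A large number of simulated infants removes Monte Carlo error. It does not remove the sampling error of inputs estimated from 400 trial infants and 300 charts, nor the uncertainty of inputs taken from the literature or from experts. The promised sensitivity analyses are tied to distant periods without data, so the 1-year result has no uncertainty analysis at all.

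Elsewhere the plan does give 95% intervals: for diagnostic proportions and their ratio (9.4.1) and for baseline descriptors such as birth weight and length of stay (9.4.5). The economic endpoints get none, although they carry the plan's only verdict-like label.

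The ranking also decides which contrasts are reported, and those need not be the contrasts in the endpoint definitions.

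**Working it through.** The plan states no SD, error rate or precision for the economic endpoints, so there is no figure of its own to reproduce. The check asks how the written rule behaves when there is nothing to find.

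**Inputs from the documents.** Three strategies and two neighbour comparisons (9.4.3); 400 trial infants (9.2), each receiving both tests (4.1); 300 chart-review infants for SOC (4.1, 9.4.3).

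**Assumptions, not in the documents.** Equal true mean cost and QALYs; normal estimation errors; equal per-infant SD across strategies; SOC errors independent of the tests' errors; error correlation between the two tests of 0 or 0.9, since they share infants; correlation between cost and QALY errors from −0.8 to 0.8.

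**Step 1, exact case.** If cost errors are exchangeable across strategies and independent of QALY errors, the costs read in QALY order are a random permutation of three values. Only one of the 3! = 6 permutations rises throughout and so earns no label. Hence P(at least one label) = 1 − 1/6 = 0.833. The standard error does not enter, so more infants would not lower this figure while the true difference is zero.

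**Step 2, simulation of the rule** (300,000 replicates per cell; n = 300 for SOC, 400 for each test). P(at least one cost-saving label):

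| Cost–QALY error correlation | Test errors uncorrelated | Test errors correlated 0.9 |
|---|---|---|
| −0.8 | 97.5% | 96.6% |
| −0.5 | 93.1% | 90.9% |
| 0 | 83.3% | 79.0% |
| 0.5 | 67.3% | 61.5% |
| 0.8 | 48.2% | 43.2% |

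A single comparison is labelled about 50% of the time with uncorrelated cost and QALY errors, and 23% to 77% over the grid. Incremental QALYs were non-negative in every replicate, as the plan says they must be.

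**Step 3, size of the apparent health gain.** For two strategies whose true QALY difference is d standard errors of the difference, the mean reported increment after sorting is 2φ(d) + d(2Φ(d) − 1).
- d = 0: √(2/π) = 0.80 SE, against a true value of 0.
- d = 1: 2(0.242) + 0.683 = 1.17, an excess of 0.17 SE.
- d = 2: an excess of 0.02 SE.

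The upward shift matters only near equality.

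**Step 4, contrasts.** Both tests are neighbours of SOC only if SOC ranks in the middle, which is 2 of the 6 possible orders. If SOC ranks lowest, the upper test is compared with the other test and not with SOC. Its point difference from SOC can be recovered by adding the two increments, but its ICER against SOC is not among the planned outputs.

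**Step 5, effect of attaching uncertainty.** As an illustration only, suppose the label required 95% intervals excluding zero for both incremental QALYs (above) and incremental cost (below). With three equal strategies, P(at least one label) falls to about 0.1% to 0.2% with uncorrelated cost and QALY errors, and to 0% to 3.1% over the grid.

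**The case against.** **Sorting is normal practice.** A reader might infer that the sort is itself the error. It is not. Ranking by effectiveness and comparing neighbours is the usual incremental analysis, and the plan discloses what it does to the sign. The gap is the missing uncertainty statement.

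**Equality is not what the plan expects.** Section 2.1 puts an rWGS trio at about $19,500 and lists lower cost among the advantages of NewbornDx. The rates above therefore describe the case of no true difference. They are not a forecast, and the documents do not show that noise will be reported as a gain. This stands. The concern is that a reader of the results could not tell the two situations apart.

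**The inputs are partly shared.** Section 9.4.3 assumes that costs and utility weights depend on health state and not on the testing technology. Differences between the tests then come from transition probabilities and test inputs, and cost and QALY errors are probably correlated. This also stands, and it is why a range is given and not 83% alone. It also rules out a dollar figure built from the average NICU cost of $76,164 in section 2.1. That is a general NICU average with no SD, and differencing raw cohort means is not the planned estimator.

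**More than a label is reported.** The sizes of the increments and the ICERs are planned outputs. A reader might infer that Hypothesis #2 in section 4.1 will be decided by the label. It concerns cost alone and uses neither the QALY ranking nor the label.

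**The plan is descriptive (9.1).** That removes any need for a test, but not for an interval. The plan's other descriptive analyses have intervals.

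**Conclusion.** The point holds as a gap in uncertainty reporting for two secondary endpoints. Followed as written, section 9.4.3 yields an unqualified statement that a strategy cuts cost and improves health, based on signs alone, with no uncertainty analysis for the 1-year result and only an unspecified one for part of the lifetime result.

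The textual findings are firm. The size is conditional on three truly equal strategies: about 83% for at least one label with independent errors, and 43% to 97.5% over the assumed correlations. These rates fall as true differences grow relative to their standard errors, and the documents give no SD or effect size from which to say where the study will lie. Separately, the planned increments include both comparisons with SOC only if SOC ranks in the middle on QALYs.

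**What to change.** Amend the cost-effectiveness paragraph of section 9.4.3 as follows.

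1. Keep the ranked incremental analysis. Add three fixed contrasts, NewbornDx versus SOC, rWGS versus SOC, and rWGS versus NewbornDx, each with incremental cost and QALYs of either sign.
2. Propagate uncertainty at both horizons. Resample infants within the trial and chart-review cohorts for inputs estimated from them, keeping each trial infant's two test results together. Use probabilistic sensitivity analysis for inputs from the literature and from experts.
3. Report 95% intervals for incremental costs and QALYs.
4. Use the cost-saving label only alongside the estimated probability that cost is lower and QALYs are not lower, at each horizon.

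No new data or infants are needed, and none of these outputs requires a willingness-to-pay value. The real cost is modelling work: distributions must be set for the disorder-group inputs drawn from literature and expert opinion. The headline will also be less tidy.

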9.4.4 SAFETY ANALYSES

All-cause mortality will be evaluated at discharge home from the hospitalization during which enrollment occurs and at one-year CGA. Data will be reviewed to determine if diagnoses are made in a timely fashion and if the diagnoses are reported accurately.

9.4.5 BASELINE DESCRIPTIVE STATISTICS

Population description: Gestational age, birth weight, day of life at admission, and length of stay in the hospital will be summarized with means, medians, standard deviations, inter-quartile ranges, and 95% confidence intervals (CI). Prenatal evaluations, complications, and mode of delivery will be summarized with frequencies and percentages. Signs/ symptoms that warranted the testing will be summarized with frequencies and percentages.

9.4.6 PLANNED INTERIM ANALYSES

Interim analyses are not planned.

9.4.7 SUB-GROUP ANALYSES

The primary or secondary endpoints will not be analyzed by demographic sub-groups; we do not expect different results according to sex or race/ethnicity.

9.4.8 TABULATION OF INDIVIDUAL PARTICIPANT DATA

N/A

9.4.9 EXPLORATORY ANALYSES

A review of the conditions detected by rWGS but not NewbornDx will be conducted and this review may potentially improve the NewbornDx panel.

10 SUPPORTING DOCUMENTATION AND OPERATIONAL CONSIDERATIONS

10.1 REGULATORY, ETHICAL, AND STUDY OVERSIGHT CONSIDERATIONS

10.1.1 INFORMED CONSENT PROCESS

10.1.1.1 CONSENT/ASSENT AND OTHER INFORMATIONAL DOCUMENTS PROVIDED TO PARTICIPANTS

Consent materials for this protocol include and the Informed Consent Form and a Secondary Findings Parent Handout, both of which will be IRB-approved prior to use. The ICF will describe in detail study procedures and risks and will include check boxes to elect to receive secondary findings for the infant and each biological parent. The same informed consent forms and when applicable, assent forms, will be used at all sites. The ICF will be translated into Spanish. Short-forms will be used for all languages other than English or Spanish.

10.1.1.2 CONSENT PROCEDURES AND DOCUMENTATION

Documentation of Consent

Written documentation of informed consent is required prior to enrolling in the study or conduct of any study procedures with the exception of IRB-approved recruitment efforts and the unusual circumstance described in #7 of the telephone consent procedures. Written documentation of consent is required for the participation by the infant and each biological parent providing a blood sample.

Consent when the Parent/Guardian of the Infant or a Biological Parent is \geq 18 Years

Participation of the infant requires written documentation of consent by one parent/guardian. Participation of a biological parent requires written documentation of consent by that biological parent.

Consent when the Parent/Guardian of the Infant is $<$ 18 Years Old

State	Who provides consent for the Infant's participation?	Must a minor parent provide assent for the infant's participation?
California	Minor parent	N/A
Massachusetts	Minor parent	N/A
New York	Minor parent	N/A
North Carolina	One guardian of the minor parent	No
Ohio	Minor parent	N/A
Pennsylvania	Minor parent	N/A

Consent when a Biological Parent is < 18 Years Old

State	Who provides consent for participation by the minor parent?	Must a minor parent provide assent for his or her own participation?
California	One guardian of the minor parent	Yes
Massachusetts	Minor parent	N/A
New York	Minor parent	N/A
North Carolina	One guardian of the minor parent	Yes, assent signature line on ICF
Ohio	One guardian of the minor parent	Yes, assent signature line on ICF
Pennsylvania	One guardian of the minor parent	Yes, assent signature line on ICF

Assent for a minor parent's participation is required by 4 sites. North Carolina Children's Hospital, Children's Hospital of Pittsburgh and Cincinnati Children's Hospital Medical Center will use an additional assent signature line on the ICF. A separate assent form for participation by a minor parent will only be used by Rady Children's Hospital - San Diego and submitted to the central IRB at the time of their site IRB application.

By signing the informed consent form, the infant's parent/guardian agrees that the infant will complete all evaluations required by the study, unless the infant's parent/guardian withdraws the infant voluntarily or the infant is withdrawn from the trial for any reason.

The original signed ICF and if applicable, assent documents, will be put in the infant's research file. A copy of the signed informed consent/assent documents will be:

- provided to the parent/guardian(s) and biological parent(s) as applicable
- put into the infant's medical record and if applicable, each parent's medical record

An entry into the infant's medical record will indicate informed consent was obtained (refer to the Documentation of Informed Consent template).

Process of Informed Consent

Informed consent is a process initiated prior to the individual's agreeing to participate in the study and continuing throughout the individual's study participation.

1. Research staff at the enrolling site will communicate with the clinical team prior to approaching a parent/guardian. The clinical genetics team will be consulted as dictated by SOC at each site. The clinicians may be asked to speak with the parent/guardian(s) prior to their approach by the research team depending on family and clinical circumstances.

2. The parent/guardian(s) of the infant and as applicable, the biological parents of the infant, will be approached directly for consent. If the parent/guardian(s) are not directly available, they may be contacted via telephone in extenuating circumstances (see telephone consent below).
3. Research staff will provide a comprehensive summary of the study including contact information for the research team, and if requested, consent/assent documents.
4. The site-PI, co-investigator or a study coordinator who is experienced in genetic studies will obtain consent. This person will verbally explain the research study and answer any questions. The information available on each genetic sequencing platform including primary findings, secondary findings and the risk of finding out about mistaken paternity or suspected incest will be described (refer to section 2.3 Risks/Benefits). The following will be emphasized: participation is voluntary; the infant may be withdrawn from the study at any time without prejudice, and the decision not to participate will in no way adversely affect the quality of their infant's medical care.
5. The parent/guardian(s) and biological parents will have the opportunity to review the written consent form and ask questions prior to signing. Parent/guardian(s) will be given as much time to consider the study and read the consent documents as necessary.

Non-English Speakers

1. For non-English speaking families, a fully translated standard consent or an oral presentation accompanied by a short form may be used to obtain informed consent. The fully translated consent and the short form will be approved by the central IRB prior to its use.
2. A Spanish translation of the informed consent form will be available; a short form will be used for all other languages. If a short form is not available for the family's preferred language, consent will be obtained through a certified interpreter and documented on the English consent form. Short forms approved by the Johns Hopkins IRB can be found here:
https://www.hopkinsmedicine.org/institutional_review_board/forms/short_form_translation.html
3. An interpreter from the hospital will be called to assist with the consent process if needed. When an interpreter is not available in-person, a professional phone interpreter service may be used. Family members should not serve as an interpreter due to the complex nature of genetic testing.
4. Interpreters may also serve as a witness to the short form consent process; their signature as an interpreter (or an interpreter reference ID number from a professional telephone interpreter service) will serve as a witness signature. The non-English speaking participant signs the short form consent in their language. The person obtaining consent signs the English version full consent. The interpreter/witness understands both languages, so signs both.
5. The parent/guardian(s) and biological parent(s) who sign the consent documents will be given a copy of these documents.

Telephone consent

It is the intention of the study team to obtain written consent from the parent/guardian for the infant and each biological parent if providing a sample whenever possible. It is anticipated that in certain circumstances, it may be necessary for the consent process to be conducted via telephone with written documentation of consent to follow.

Examples of when this might be needed include: when the biological mother remains at the birthing hospital after her infant is transferred to the enrolling site and a parent/guardian or biological parent cannot physically visit because the family lives too far away. If the consent process is not able to be conducted in-person, telephone consent may be used with written documentation of consent to follow.

The PI will ensure the procedures for securing telephone consent are followed:

1. The absent party will be contacted by phone. The research staff will explain the entire research study and the process required for consent by telephone. An email address or fax number will be obtained in order to forward the consent document(s). A time will be scheduled for a full informed consent when both parties will be able to have the consent physically in front of them to sign. For non-English speaking persons, refer to procedures for Non-English speaking persons above.
2. The consent document(s) will be sent to the absent party. The absent party will be advised that they are welcome to read this document, but they will be asked not to sign the document until the time of the scheduled consent.
3. At the time of the scheduled consent, the research staff will have a witness present to confirm that the telephone consent was conducted. All study information will be discussed, and any questions answered.
4. Following the explanation of the study, the absent party will be asked to sign and date the document. The research staff and witness will also sign and date their copy.
5. The absent party will be asked to return the signed document to the research team, either electronically or if necessary, by mail.
6. Copies of both signed documents will be made and returned to the absent party.
7. Written documentation of consent will be obtained prior to any study activities with one exception. In the circumstance where testing is urgent (clinical situation is life-threatening) and written documentation of consent is not readily feasible (i.e. no access to a fax machine or scanner), verbal consent as documented by the research staff will be sufficient to obtain, ship and process blood samples. However, written documentation of consent by the parent/guardian must be documented prior to the return of any results.
8. If necessary, the research staff will attempt to arrange for a blood collection kit to be delivered to the absent party. In the case where the biological mother is at another hospital and wishes to provide a blood sample, we will work with the birthing hospital to collect the sample and return the consent documentation.
9. The consent will be documented per hospital and IRB policies.

New Information

Any new information that may affect willingness to continue in the study will be communicated by the investigator to the parent/guardian(s) or biological parent(s) in

accordance with IRB requirements. The informed consent document will be updated and re-consent will be obtained if necessary.

Waiver of Consent

Waiver of consent is requested for the clinician survey. After the genomic sequencing result is returned for an infant, the physician of record for the infant will complete a survey about changes in care from study results and perceived utility of testing.

